4.3 Subject Recruitment and Screening

Subjects will be offered participation in the study during their visit to the Women’s Imaging Center by the PIs, [name], [name], and/or their designee. This study may recruit up to 1000 subjects. Patient’s will be eligible for study participation if they have a scheduled visit for the Women’s Imaging Center and have not previously participated in this study. The reason for the patient’s visit, screening or diagnostic, will not affect their eligibility. Diagnostic visits are included as it is necessary to ensure the accuracy of the iBE device’s ability to detect BIRADs 3-5. The iBE device was created to use as a screening tool to detect clinically relevant breast lesions, defined here as BIRADs 3-5, with the purpose of giving patients proper follow-up recommendations without causing unnecessary anxiety of avoidable diagnostic tests.

5 Study Procedures

Participants will be recruited from the Women’s Imaging Center who are scheduled to undergo screening or diagnostic imaging including biopsies. Subjects will have the study explained to them and given the consent form to review early in their imaging center visit. After the subjects have had time to review the consent, the PI or designee will answer all questions. If she/he agrees and signs the consent form, they will receive a signed copy to take home with them. All subjects must meet the inclusion and exclusion criteria. Consent will be obtained prior to any study-related activities.

The iBE evaluation will be performed by a trained individual who is blinded to the outcome of the radiology studies at the time the iBE is performed. The trained individual will be a healthcare worker with minimum education (or equivalence) to a licensed practical nurse (LPN) or an ultrasound tech. This is the target education level for the intended iBE operators. The selected healthcare worker will be trained by [name], MD to administer the iBE and clinical breast exams. The trainee will follow [name] during clinic hours for 1-2 days and trained for clinical breast exams, similar training to a medical student. The iBE training will mostly be software and instrument training by the leading iBE user in the United States, [name]. A minimum of two healthcare workers will be trained.

[figure not shown]

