Subjects will be scanned with the iBE device administered by the trained individual while in a supine position without breast immobilization similar to ultrasound testing. A bilateral iBE exam will be performed on the entire breast as well as a bilateral Clinical Breast Exam (CBE) the findings will be documented on the case report forms and the device tablet concurrently.

If the patient is selected to participate in the inter-rater reliability portion of the study, the subject will undergo both the iBE and the clinical breast exams twice performed by two different separately trained individuals sequentially during the same visit. The trained individuals will have their own case report forms and tablets that integrate to the iBE to prevent results sharing and bias. The selection for the inter-rater reliability portion of the study will be decided by the day of the week. The second trained individual will be present one a day week and that day all the patients will be asked to participate in the dual exam inter-rater reliability portion of the study.

These data are recorded and processed by an automated software algorithm and the results are displayed topographically on a “breast-map” with red areas showing positive findings and green areas showing negative findings. All the recorded data are collected on the tablet without HIPAA identifying variables. The tablet will assign a four digit subject number incrementally increasing for each subject prior to the iBE scan and this number will be recorded on the case report form. Results of the test will be reported to the patient as well as the radiology technologist and radiologist. The iBE evaluation may add between 10 and 30 minutes to the clinic visit. The iBE evaluation will be done prior to the patient’s original scheduled imaging visit. After the completion of the imaging visit the radiologist will evaluate the images and the iBE report. If there are areas identified on the iBE that are not resolved by the scheduled mammogram an ultrasound will be performed in the area of concern (if not already scheduled).

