6.2 Statistical Methods

Data will be analyzed using contingency table methods, estimating the sensitivity and specificity of the device to correctly assign subjects to BIRADS 1, 2 versus BIRADS 3, 4, 5 categories. Sensitivity is calculated from contingency table counts as $TP/(TP+FN)$, and specificity is calculated as $TN/(TN+FP)$, (and will be log transformed) with variances obtained using the delta method. Both sensitivity and specificity measures are expected to be high, given great performance in preliminary data (0.95 and 0.92 respectively). We will use a non-inferiority approach, attempting to demonstrate that in the clinical setting, iBE matches our preliminary values, and we will test them against null hypothesis values (Non inferiority boundaries) that are 5% below our preliminary data using the z-score for the log-transformed measure.

	Mammogram BIRADS 1,2	Mammogram BIRADS 3,4,5 or biopsy positive (same breast and same quadrant)
iBE negative	True Negative (TN)	False Negative (FN)
iBE positive	False Positive (FP)	True Positive (TP)

And to CBE as a primary comparison

	CBE negative	CBE positive
iBE negative	True Negative	False Negative
iBE positive	False Positive	True Positive

7 Safety and Adverse Events

Due to the nature of this device and our experience thus far, adverse effects are not anticipated, however, the investigator will follow the processes below should an event occur.

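### Section 5 sets no order between iBE and CBE and does not lock the CBE result before the iBE map is seen, so the CBE comparison in section 6.2 is open to carry-over of unknown size.

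*Combined protocol and SAP*

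**What the plan says.** Section 5 (Study Procedures) describes the exams in one sentence: "A bilateral iBE exam will be performed on the entire breast as well as a bilateral Clinical Breast Exam (CBE", and adds that "the findings will be documented on the case report forms and the device tablet concurrently". The healthcare worker who operates the device is trained "to administer the iBE and clinical breast exams". For the inter-rater subset, "the subject will undergo both the iBE and the clinical breast exams twice performed by two different separately trained individuals", one after the other at the same visit. On timing of that subset: "The second trained individual will be present one a day week".

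Two kinds of masking are stated. The iBE operator is someone "who is blinded to the outcome of the radiology studies at the time the iBE is performed". On dual-exam days, each operator has a separate case report form and tablet.

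One order is stated, that of iBE against imaging: "The iBE evaluation will be done prior to" the scheduled imaging.

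Section 1.4 says the device shows its findings in real time. Section 5 says iBE is scored by an automated algorithm and shown as a red and green map, and that CBE is entered on the touch screen as a similar map. Section 6.2 gives a second contingency table, with CBE in the reference position, under the words "And to CBE as a primary comparison". Section 3.2 lists iBE accuracy against imaging or biopsy, and inter-rater reliability; it lists no CBE endpoint.

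**The concern.** A comparison of two tests on the same subject needs each result to be reached without knowledge of the other. Here one operator appears to produce both, on similar map displays, with entry at the same time. iBE is scored by software. CBE is a judgement, and section 1.2 itself cites calls to reduce its subjectivity. If the iBE map is visible before CBE is decided or entered, an area shown in red invites a positive CBE call at the same place. The CBE result then partly repeats the iBE result.

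At stake is the CBE comparison, in whichever form it is analysed. A contaminated CBE entry cannot be separated from a clean one after data collection, so this has to be settled in the procedure.

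**Working it through.** **Text check.**

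- *Who:* both exams by each operator is explicit on dual-exam days. For other days the sentence is passive, but the workers are trained in both exams and the second worker attends one day a week. One operator for both exams is the natural reading.
- *Order:* iBE is ordered against imaging, and the two operators are ordered against each other. CBE is not ordered against iBE.
- *Masking:* from radiology, and between operators. None is stated between one operator's two exams.
- *Locking:* none is stated.
- *Not visible to this review:* Scheme 1, a figure in section 5 and the case report form. Any of them might show an order.

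**Illustration of direction and scale.** The documents give no carry-over figure to reproduce. Inputs:

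- iBE sensitivity 0.95 and specificity 0.92 (section 6.2).
- CBE 0.50 and 0.94 (assumed from the benchmark in section 1.3, which is not given for this population).
- 20% of subjects BIRADS 3-5 (assumed; section 6.1 says only that 80% of screening mammograms are BIRADS 1 and 2).
- c, the share of iBE-positive, CBE-negative calls upgraded to CBE-positive (assumed, no source).

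Cells, with the two exams independent given true status:

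- iBE+/CBE+: a = 0.2×0.95×0.50 + 0.8×0.08×0.06 = 0.0988
- iBE+/CBE−: b = 0.2×0.95×0.50 + 0.8×0.08×0.94 = 0.1552
- iBE−/CBE+: d = 0.2×0.05×0.50 + 0.8×0.92×0.06 = 0.0492
- iBE−/CBE−: e = 0.2×0.05×0.50 + 0.8×0.92×0.94 = 0.6968

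At maximum dependence (joint positives equal to the smaller marginal), the cells are 0.148, 0.106, 0 and 0.746.

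*CBE as reference (the section 6.2 table).* Carry-over moves c×b from the second cell to the first:

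- sensitivity = (a + cb)/(a + cb + d)
- specificity = e/(e + (1−c)b)

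| c | Independence: sens / spec | Maximum dependence: sens / spec |
|---|---|---|
| 0 | 0.668 / 0.818 | 1.00 / 0.876 |
| 0.10 | 0.699 / 0.833 | 1.00 / 0.887 |
| 0.20 | 0.725 / 0.849 | 1.00 / 0.898 |
| 0.50 | 0.782 / 0.900 | 1.00 / 0.934 |

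Specificity always rises. Sensitivity rises unless d is zero. At c = 0.20 the shifts are 0 to +0.058 and +0.022 to +0.031. For scale, the 95% half-widths with 1000 subjects under independence are 1.96×√(0.668×0.332/148) = 0.076 for sensitivity and 1.96×√(0.818×0.182/852) = 0.026 for specificity.

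*Both exams scored against imaging.* Under independence, observed CBE sensitivity = 0.50 + c×0.95×0.50. At c = 0.20 this is 0.595, and the iBE advantage falls from 0.95 − 0.50 = 0.45 to 0.95 − 0.595 = 0.355. At maximum dependence it is 0.50 + 0.20×0.45 = 0.59, and the advantage is 0.36. Observed CBE specificity also falls, from 0.94 to 0.94 − 0.20×0.08×0.94 = 0.925 under independence. So on sensitivity the error works against the device, the reverse of the section 6.2 table.

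**The case against.** The strongest reply is that the weight is small. The CBE comparison is in neither the objectives (section 2) nor the endpoints (section 3.2); its only support is the line above a table in section 6.2, with no test, margin or hypothesis. In the illustration, using CBE as reference already turns 0.95/0.92 into 0.668/0.818 with no carry-over at all, a far larger gap than the shift at c = 0.20. This stands, and it limits the point to a cheap improvement.

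A second reply is that c has no source and the grid is only as good as its inputs. This also stands. Section 1.2 gives 28-36% for CBE efficacy in practice; if 0.28 is read as sensitivity, the independence figure at c = 0.20 goes from 0.548 to 0.673, a larger shift. The numbers show direction and rough scale only.

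A third reply is that putting CBE first exposes a listed endpoint, iBE accuracy, to the operator's knowledge of the CBE result in order to protect an unlisted comparison. The trade-off is real and its size cannot be derived from the documents. However, the present silence already permits that exposure whenever CBE happens to come first.

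Four stronger readings are tempting, and the documents do not support them:

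- *Section 5 does not say who performs CBE.* It points to the trained worker, explicitly on dual-exam days.
- *CBE is in fact done after iBE, or is contaminated.* The text leaves this open, and material not seen might settle it.
- *Carry-over always flatters the device.* The direction depends on the analysis.
- *The main accuracy result is compromised.* iBE findings prompting CBE calls do not change the algorithm's iBE result.

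**Conclusion.** The point holds as an open procedural gap. The text sets no order between iBE and CBE and has no rule that CBE is locked before the iBE map is seen, while one operator appears to do both exams.

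The size is unknown. On the assumptions shown, a 20% upgrade rate moves the section 6.2 table by 0 to +0.058 in sensitivity and by +0.022 to +0.031 in specificity; the specificity shift is about as large as its sampling error. The same rate cuts the iBE sensitivity advantage against imaging from 0.45 to about 0.36. The listed iBE-versus-imaging endpoint is not affected in this direction.

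The conclusion rests on the text alone and would fall away if Scheme 1, the figure or the case report form sets an order and a lock. It is worth correcting because the change is cheap and the data cannot be repaired later. Whether CBE is an endpoint is a separate inconsistency and adds nothing to the weight of this one.

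**What to change.** In section 5, fix the order of the two exams. Require each result to be completed, locked and timestamped before the next exam begins, with no later edits. State in the main-cohort sentence that the same worker does both, if that is the intent.

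Completing the subjective CBE first, then the whole-breast, algorithm-scored iBE scan, protects the CBE comparison. The cost is wording in the protocol and case report form plus a timestamp, with no extra staff or exams. The downside is that the operator knows the CBE result while scanning, which could affect the listed iBE endpoint through how the probe is placed or pressed. Whole-breast scanning and automated scoring limit this by an amount that the documents do not allow one to estimate.

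If that risk is judged the greater, randomise and record the order. About half of the scans are then exposed to a known CBE result, but about half of the carry-over remains in the pooled table: c = 0.20 acts as 0.10, giving sensitivity 0 to +0.032 and specificity +0.011 to +0.015 on the assumptions above.

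Separately, reconcile section 3.2, which lists no CBE endpoint, with section 6.2, which treats the CBE comparison as primary.

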3.2 Study Endpoints

- To determine the sensitivity and specificity of iBE exams for the detection of clinically relevant breast lesions (defined as BIRADS 3-5 on imaging, and/or malignant on biopsy).
- To determine inter-rater reliability in the iBE production prototype.

4 Subject Selection

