The current pathway of breast lesion detection can be modified in this protocol in order to ascertain the accuracy of the iBE device illustrated in Scheme 1 below. The current pathway of breast lesion screening and detection begins with a screening mammogram or a diagnostic mammogram/ultrasound. If nothing is detected by mammogram or ultrasound then the pathway is complete and a follow-up recommendation is given. However, if something suspicious is detected by the initial mammogram then additional imaging is requested such as an ultrasound. If the additional ultrasound reveals something suspicious a biopsy maybe recommended for confirmation or if a benign finding is revealed a follow-up recommendation is be given. The addition of iBE screening will only modify the current pathway if the iBE exam returns a positive result when the initial mammogram provides a negative result. If this occurs a study provided ultrasound will be recommended and the ultrasound’s results will be used to verify the iBE positive result. If the ultrasound invalidates the iBE positive result, it will be deemed a false positive and the diagnostic tests are complete. However, if the ultrasound confirms the iBE’s result [name] and the radiologist will discuss if further diagnostic intervention (i.e. biopsy) is required. Data on the final disposition of the imaging, any biopsies and any follow up imaging to 18 months after participation will be recorded in the database.

Scheme 1: Current Algorithm with Integrated Study Pathway

Quantitative Data

Quantitative data from the test will be documented and analyzed for accuracy metrics.

The iBE device collects only compression measurements and stores these data on the mobile device. Compression data are recorded for our records and a copy is available to UELS via Dropbox, which is backed up online and offsite.

We know the data are captured accurately because a unique file gets created at the end of every scan in a specific folder inside the DELL tablet. The app gives the user a notification that the data were saved properly to the tablet at the end of each scan.

The data sent to the UELS database are identical to those on the tablet, as they are synced between the folder inside the tablet and Dropbox. This ensures that an exact copy of the files created at the site are sent to UELS. These files use a unique ID entered by the user and have no identifiable patient information.

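### The visible text does not require BIRADS to be recorded before the radiologist sees the iBE report, and sections 3.2 and 6.2 score ultrasound-only lesions in opposite ways

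*Combined protocol and SAP*

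**What the plan says.** **Masking and order (section 5).** The iBE exam is done before the scheduled imaging by "a trained individual who is blinded to the outcome of the radiology studies at the time the iBE is performed". Its result then travels: "Results of the test will be reported to the patient as well as the radiology technologist and radiologist". After imaging, "After the completion of the imaging visit the radiologist will evaluate the images and the iBE report".

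**Added ultrasound (section 5).** Where there are "areas identified on the iBE that are not resolved by the scheduled mammogram an ultrasound will be performed in the area of concern". The iBE exam "will only modify the current pathway if the iBE exam returns a positive result when the initial mammogram provides a negative result", and the ultrasound's "results will be used to verify the iBE positive result". An iBE result that the ultrasound invalidates is labelled a false positive. No label is given to one that it confirms. On what is kept: "Data on the final disposition of the imaging, any biopsies and any follow up imaging to 18 months after participation will be recorded".

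**Reference standard.** Section 3.2 defines a clinically relevant lesion as "defined as BIRADS 3-5 on imaging, and/or malignant on biopsy", without restricting the modality. The 6.2 contingency table instead heads its positive column with mammogram BIRADS 3, 4 or 5 or a positive biopsy, matched on breast and quadrant. Ultrasound is not named there.

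**Targets (6.2).** Expected sensitivity and specificity are 0.95 and 0.92. Each is tested against a boundary 5% lower by a z-score on the log scale. Alpha is not given, nor is whether 5% is absolute or relative.

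**The concern.** Two things can move specificity without any change in the device.

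(a) If the person assigning BIRADS already knows that iBE is positive in a quadrant, a borderline reading may be raised to 3. That turns an iBE false positive into a true positive.

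(b) With two reference definitions in force, the same data yield two specificities, and the choice between them could be made after the results are seen.

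A smaller matter: (c) 6.2 speaks of assigning subjects but its table matches on breast and quadrant. The scoring of an iBE-positive area away from the lesion is therefore not settled.

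Section 2 wants validated accuracy values in preparation for an international trial, so both the estimates and their definition matter.

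**Working it through.** **The plan's own figures.** Boundaries: 0.95 − 0.05 = 0.90 and 0.92 − 0.05 = 0.87 if absolute; 0.95 × 0.95 = 0.9025 and 0.92 × 0.95 = 0.874 if relative. The 80% power in 6.1 cannot be reproduced, because alpha, sidedness and the number of reference-positive subjects are not stated. Nothing below depends on it.

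**Assumptions for illustration.** 200 lesions and 800 non-lesions (6.1 gives 80% BIRADS 1-2 for screening mammograms only, and the enriched study mix is not stated); boundary 0.87; exact one-sided test at 0.025. The plan's log-scale statistic is z = ln(p/0.87) / √[(1−p)/(np)], compared with 1.96.

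**(a) Reading influence.** Put true values at the boundaries: TP 180, FN 20, TN 696, FP 104. Let a fraction f of iBE false positives be raised to BIRADS 3-5.
- Specificity = 696/(800 − 104f). At f = 5%: 696/794.8 = 0.876. At f = 10%: 696/789.6 = 0.881.
- Chance of clearing 0.87: 2.4% with no influence, about 6% at f = 5%, about 14.5% at f = 10%.
- Sensitivity = (180 + 104f)/(200 + 104f): 185.2/205.2 = 0.903 and 190.4/210.4 = 0.905, so it hardly moves. If 10% of iBE-negative lesions were also lowered to BIRADS 1-2, it would read 190.4/208.4 = 0.914.

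**(b) Two references.** Take an iBE-positive, mammogram-negative lesion graded BIRADS 3-5 on ultrasound, without a positive biopsy.

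| Text | Score |
|---|---|
| 3.2 | true positive |
| 5 | not labelled; true positive implied |
| 6.2 table | false positive |

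The conflict needs the ultrasound itself to be BIRADS 3-5. If it confirms only a benign finding, 3.2 and the table agree on false positive. A lesion seen only on a scheduled ultrasound meets the same conflict.

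Let k be the number of such lesions, 95% of them iBE-positive.

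*If 0.92 is the 3.2 value*, table specificity = (736 + 0.05k)/(800 + k):

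| k | Table specificity | Passes 0.87, exact | Passes 0.87, log z |
|---|---|---|---|
| 0 | 0.920 | over 99% | over 99% |
| 10 | 736.5/810 = 0.909 | 95% | 97% |
| 20 | 737/820 = 0.899 | 72% | 80% |
| 40 | 738/840 = 0.879 | 5% | 9% |

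With the relative boundary of 0.874 the exact figures are 90/58/2% at k = 10/20/40.

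*If 0.92 is the table value*, 3.2 specificity = (736 − 0.05k)/(800 − k): 735.5/790 = 0.931, 735/780 = 0.942, 734/760 = 0.966. The table itself clears 0.87 with over 99% probability, so both references pass.

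Near the boundary an observed result can flip. Table specificity 704/800 = 0.880 gives z = 0.88 and fails. Moving 19 of its 96 false positives to true positives gives 704/781 = 0.901, z = 3.00, and passes.

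**Sensitivity and selective verification.** Only iBE-positive, mammogram-negative subjects get the study ultrasound. If a share m of lesions is occult to usual care, and so counted only when iBE is positive, true sensitivity 0.90 reads 0.90/[0.90 + 0.10(1 − m)]: 0.905 at m = 5% and 0.909 at m = 10%.

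**The case against.** **On reading order.** The rule for added ultrasound presupposes an initial mammogram result, the radiologist sees the iBE report only after imaging is complete, and Scheme 1 may show the sequence. All fair: the gap is an omission in the visible text. But a result that must exist is not one that must be recorded first, and the imaging outcome kept in the database may postdate the iBE report. A reader might infer that readings will be influenced, or that both accuracy measures are inflated. The documents do not support that: the 5% and 10% rates are assumed, and raised readings alone barely move sensitivity.

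**On the two references.** The word mammogram in the table could be loose shorthand for imaging. Section 2 weighs against this, since it too names mammography-based screening as the comparator. It is true that section 5 only implies a true positive for a confirmed finding; the firm contradiction is between 3.2 and the table.

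**On size.** A reader might infer that power falls to 72% or 5%. That holds only if 0.92 belongs to the 3.2 reference, and 6.2 does not say which reference produced it. Nor can k be taken from the earlier series in 1.6. Subtraction there gives 5 of 27 lesions in women over 40 not counted as mammographically visible, but that is not the same as ultrasound BIRADS 3-5 without a positive biopsy. The series reports no BIRADS grades and used an older probe.

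**On unit.** Assigning subjects with a quadrant match can be a coherent subject-level rule. Only the off-target positive is left undefined.

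**Conclusion.** The point stands on the text. The order of reading is not fixed, and 3.2 and the 6.2 table contradict each other on ultrasound-only BIRADS 3-5 lesions without a positive biopsy. Specificity is exposed to upward bias from the first and has two values because of the second. The size cannot be determined: it depends on an unknown number of such lesions, on an assumed 800 non-lesions and alpha, and on which reference the 0.92 describes. The pass/fail conclusion changes only when specificity lies near the boundary. The documents do not show that the trial will be biased or underpowered. Both gaps should still be closed before data accrue, because a BIRADS reading not recorded before the iBE report is seen cannot be recovered in analysis. The unit of analysis is a minor addition.

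**What to change.** 1. For every subject, record and time-stamp BIRADS by breast and quadrant from usual-care imaging before the reading radiologist sees the iBE report. Withhold the iBE result from the technologist until the scheduled images are acquired. Usual-care imaging means the scheduled mammogram or ultrasound, any ultrasound prompted by the mammogram itself and, for biopsy visits, the prior imaging that led to the biopsy. The iBE-triggered pathway then continues as written.
2. Use one primary reference, worded identically in 3.2, 5 and 6.2. Report the other scoring in a pre-specified second table, with the number of lesions reclassified. Locked usual-care BIRADS 3-5 or malignant biopsy is suggested as primary, because the iBE-triggered ultrasound can add true positives but never false negatives. The broader reference is also defensible. State which reference the 0.95, the 0.92 and the 5% boundaries refer to.
3. State that sensitivity is relative to this reference, because subjects negative on both tests get no added ultrasound. Report the 18-month follow-up by iBE result as supportive.
4. State the unit of analysis and how an off-target iBE positive is scored.
5. Reconcile section 2, which says the project will not affect clinical decisions, with the iBE-triggered pathway in section 5.

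**Cost.** One time-stamped field and revised wording, with no added reader, imaging or subjects. The iBE result is seen slightly later in the visit, and primary specificity may be lower. Subjects negative on both tests remain unverified: this is disclosed, not cured.

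### In mammogram-negative subjects with no ultrasound or biopsy already scheduled, only a positive iBE triggers verification, so sensitivity is biased upward by an amount the documents do not fix

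*Combined protocol and SAP*

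**What the plan says.** **Trigger.** Section 5 (Study Procedures) places iBE before the scheduled imaging. If the mammogram does not resolve an area that iBE marked, "an ultrasound will be performed in the area of concern (if not already scheduled"). The pathway description repeats the rule: adding iBE "will only modify the current pathway if the iBE exam returns a positive result when the initial mammogram provides a negative result". If the ultrasound does not confirm the iBE finding, the result is a false positive. If it does, biopsy is discussed. The text gives no matching study ultrasound for a negative iBE, or for a positive CBE, although every subject has a CBE.

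**Verification that does not depend on iBE.** The standard pathway "begins with a screening mammogram or a diagnostic mammogram/ultrasound". Also, "if something suspicious is detected by the initial mammogram then additional imaging is requested such as an ultrasound". Section 5 recruits people "scheduled to undergo screening or diagnostic imaging including biopsies". Biopsies and follow-up imaging are recorded to 18 months, but no rule says whether they can change a subject's classification.

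**Reference standard.** Section 3.2 describes a relevant lesion as "defined as BIRADS 3-5 on imaging, and/or malignant on biopsy". The reference-positive column in 6.2 is "Mammogram BIRADS 3,4,5 or biopsy positive (same breast and same quadrant"). A second 6.2 table, introduced by "And to CBE as a primary comparison", sets iBE directly against CBE.

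**Reading.** Section 5 has the radiologist evaluate the images together with the iBE report.

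**The concern.** The index test decides who receives the second reference test. Take two women at a screening visit with the same mammographically occult lesion. The iBE-positive woman has an ultrasound, perhaps a biopsy, and can become a true positive. The iBE-negative woman has neither and is counted as a true negative. Each occult lesion that iBE finds can add one to both TP and TP+FN; each one it misses adds nothing to FN. This is partial verification with a known direction.

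Both reference definitions can admit lesions found this way, so reconciling 3.2 with 6.2 does not remove the problem. It does change its size. Under 3.2 a BIRADS 3–5 ultrasound is enough. Under the 6.2 table the lesion counts only if biopsy is positive.

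The trial tests sensitivity against a boundary 5% below its preliminary value, so an excess of even a point or two uses up part of the margin.

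**Working it through.** The plan gives no figure for this bias, so there is none to reproduce.

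**Inputs from the documents**
- Expected sensitivity 0.95 and specificity 0.92; boundary 5% below (6.2). The sensitivity boundary is 0.90 if absolute, 0.95 × 0.95 = 0.9025 if relative. The specificity boundary is 0.87 or 0.92 × 0.95 = 0.874.
- 1000 subjects; 80% of screening mammograms are BIRADS 1 or 2 (6.1).
- Earlier in vivo counts: 40/46 lesions found overall, 24/29 among mammographically visible ones (1.6).

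**Assumptions**
- 200 mammogram-positive and 800 mammogram-negative subjects. This applies the screening split to an enrolled mix whose split is not stated.
- *o* = 8, 24 or 40 occult lesions (1%, 3%, 5% of 800), of which iBE finds a share *s*.
- None of the 800 has other verification, and every occult lesion found is confirmed. Both are worst cases.

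**Step 1. Sensitivity.** Let *A* be the true positives among the 200.
- Plan as written: (A + s·o)/(200 + s·o)
- Standard-pathway reference: A/200
- All lesions: (A + s·o)/(200 + o)

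| A/200 | s | o | Plan | All lesions | Excess over standard pathway (points) | Excess over all lesions (points) |
|---|---|---|---|---|---|---|
| 0.85 | 0.50 | 8 | 174/204 = 0.853 | 174/208 = 0.837 | 0.3 | 1.6 |
| 0.85 | 0.50 | 24 | 182/212 = 0.858 | 182/224 = 0.812 | 0.8 | 4.6 |
| 0.85 | 0.50 | 40 | 190/220 = 0.864 | 190/240 = 0.792 | 1.4 | 7.2 |
| 0.85 | 0.85 | 8 to 40 | 0.855 to 0.872 | 0.850 | 0.5 to 2.2 | 0.5 to 2.2 |
| 0.95 | 0.95 | 8 to 40 | 0.952 to 0.958 | 0.950 | 0.2 to 0.8 | 0.2 to 0.8 |
| 0.95 | 0.50 | 8 to 40 | 0.951 to 0.955 | 0.933 to 0.875 | 0.1 to 0.5 | 1.8 to 8.0 |

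**Step 2. The documents' own counts.** Subtraction leaves 46 − 29 = 17 other lesions, of which 40 − 24 = 16 were found (94%). If those 17 were not seen on mammography (an assumption), full verification gives 40/46 = 87.0%. An iBE-triggered rule drops the one miss and gives 40/45 = 88.9%, or +1.9 points.

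**Step 3. Effect on the boundary test.** Suppose true sensitivity against all lesions is 0.90, there are 200 lesions in all, a share *q* is occult and equally detectable, and a share *v* of the missed occult ones is found independently of iBE. Observed sensitivity is *p* = 0.90/d, with d = (1 − q) + 0.9q + 0.1qv. The log-scale standard error is √[(1 − p)/(np)], with n = 200d. The chance of a false success at one-sided 5% (the plan states no alpha) is Φ[ln(p/0.90)/SE − 1.645].

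| q | v = 0: p, error | v = 0.5: p, error |
|---|---|---|
| 5% | 0.9045, 7.7% | 0.902, 6.2% |
| 10% | 0.909, 11.6% | 0.9045, 7.7% |
| 20% | 0.918, 24.3% | 0.909, 11.6% |

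With v = 1 the bias is zero.

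**Step 4. Specificity.** With true specificity 0.92, TN = 0.92(800 − o) + (1 − s)o. The plan divides by 800 − s·o; for s = 0.5 and o = 8 to 40 this gives 0.920 to 0.922, so the plan's bias is small. Counting iBE-triggered confirmed subjects as false positives divides by 800 instead: 0.916 to 0.899 for s = 0.5, and 0.911 to 0.876 for s = 0.95.

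**The case against.** **Verification is not wholly dependent on iBE.** Diagnostic visits can include ultrasound or biopsy whatever iBE shows, so an occult lesion missed by iBE can enter there as a false negative. A reader might infer that occult lesions can never count against iBE. The documents do not support that: the statement fits only mammogram-negative subjects without such scheduled work-up, at the index visit. The 18-month record might also reveal misses, but the plan schedules no such imaging and gives no rule for using it. This objection narrows the point and stands to that extent.

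**The larger figures rest on unsourced inputs.** The documents give no occult share and no support for 50% detection; the in vivo counts, read as in step 2, point to about 94%. Section 6.1 puts malignancy at 1–2% of screening mammograms. If positive biopsy means malignant, occult rates of 3–5% at screening visits are hard to reach under the 6.2 table and need the wider 3.2 definition. This stands: the excesses of 4.6 points and more in the table are scenarios, not estimates.

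**The yardstick may be the standard pathway.** Section 2 sets out to validate iBE using the results of current mammography-based screening. On that yardstick the excess with half found is 0.3 to 1.4 points, not 1.6 to 7.2. This also stands, but the plan as written does not deliver that quantity either, because it lets iBE-triggered lesions in.

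**The CBE table is untouched.** A reader might infer that the planned iBE-by-CBE comparison is tilted towards iBE. It is not: that table crosses the two tests directly, and ultrasound and biopsy do not enter it. Only an accuracy comparison of both tests against imaging or biopsy would be tilted, because the text provides study work-up only for iBE's extra findings. Scheme 1 could not be read for this review.

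**Conclusion.** The point holds for mammogram-negative subjects without an ultrasound or biopsy already scheduled. In them, verification at the index visit depends on iBE, both reference definitions can admit what it finds, and 6.2 makes no correction. The direction is upward; the size cannot be fixed from the documents.

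- **Against a standard-pathway reference:** 0.3 to 1.4 points at sensitivity 0.85 with half the occult lesions found, and 0.5 to 2.2 points if 85% are found.
- **Against all lesions:** 0.2 to 0.8 points if iBE performs at 0.95 on occult lesions too, and 1.8 to 8.0 points (visible-lesion sensitivity 0.95) if it finds only half.

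These rest on the assumed 200/800 split, 1–5% occult, no other verification and every find confirmed. Independent verification reduces them, and so does the 6.2 definition if fewer finds are biopsy-positive. The size therefore also depends on whether 3.2 or 6.2 governs. The change is worth making because the margin is narrow and the cost is small.

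**What to change.** 1. In 6.2, define the reference for the primary sensitivity and specificity tests from imaging and biopsies done regardless of the iBE result. Record the standard-pathway BIRADS category before the iBE report is seen; otherwise the reference reading is not independent of iBE.
2. Add a CRF flag for ultrasound or biopsy triggered by iBE. Leave lesions confirmed only by that route out of TP and report them separately as additional iBE yield.
3. For the specificity boundary test, count those subjects as false positives. Report the version that excludes them as a sensitivity analysis.
4. Add a sensitivity analysis that reclassifies all subjects, whatever their iBE result, from the biopsies and follow-up imaging already recorded to 18 months.
5. State that the estimate is accuracy against the standard mammography-based pathway, not against all lesions. With A/200 = 0.85, the change returns 0.85 and removes the 0.3 to 1.4 points; it does not close the gap to all lesions.
6. Use the same iBE-independent reference for any accuracy comparison of iBE with CBE, and reconcile 3.2 with the 6.2 table.

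**Cost.** SAP wording, one CRF flag and a rule on the order of recording. Sensitivity becomes slightly less favourable. Primary specificity becomes conservative: in step 4 it falls as low as 0.876, close to the 0.87 or 0.874 boundary, so that choice should be made knowingly. The clinical pathway is unchanged.
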